#### D.2.b. BREXPIPRAZOLE

Brexipiprazole (Rexulti®) is a serotonin-dopamine activity modulator, with a unique receptor binding profile and low intrinsic D2 activity suggestive of a lower potential than aripiprazole to cause activation-like adverse effects, such as akathisia (McKeage K, 2016). The drug was recently approved by the US FDA for adjunctive therapy with antidepressant treatment (ADT) in patients with major depressive disorder (MDD) and inadequate response to ADT. In two phase III trials, adjunctive oral

brexpiprazole 2 or 3 mg once daily was more effective than monotherapy with ADT in improving depressive symptoms in adults with MDD who demonstrated an incomplete response to previous treatment with ADT (McKeage K, 2016). Adjunctive brexpiprazole was generally well tolerated in clinical trials, which included treatment periods of up to 52 weeks (McKeage K, 2016). There is preliminary evidence that adjunctive treatment with brexpiprazole may represent a strategy for patients with MDD and inadequate response to antidepressant treatment who have symptoms of irritability (Fava M et al, 2016) and anxiety (McIntyre RS et al, 2016).

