#### H.2.b. EXCLUSION CRITERIA

A potential participant will NOT be eligible for participation in this study if any of the following criteria are met:

1. Female of childbearing potential who is not willing to use one of the specified forms of birth control during the study.
2. Female that is pregnant or breastfeeding.
3. Female with a positive pregnancy test at screening or baseline.
4. History during the *current* MDE of failure to achieve satisfactory response (e.g., less than 50% improvement of depression symptoms) to >7 treatment courses of a therapeutic dose of an antidepressant therapy of at least 8 weeks duration, according to the MGH ATRQ, as confirmed by the remote, independent MGH CTNI rater.
5. Total MADRS score of <20 at the screen visit or the baseline visit, or as assessed by the remote, independent MGH CTNI rater and reported to the site.
6. Current diagnosis of a substance use disorder (abuse or dependence, as defined by DSM V-TR™), with the exception of nicotine dependence, at screening or within 6 months prior to screening.
7. Current Axis I disorder, diagnosed at screening with the use of the Structured Clinical Interview for DSM-5 AXIS I Disorders (SCID-5), that is the principal focus of treatment and MDD the secondary focus of treatment for the past 6 months or more.
8. History of bipolar disorder, schizophrenia or schizoaffective disorders, or any history of psychotic symptoms in the current or previous depressive episodes.
9. History of anorexia nervosa, bulimia nervosa, or eating disorder not otherwise specified, within 5 years of screening.
10. Any Axis I or Axis II Disorder, which at screening is clinically predominant to their MDD or has been predominant to their MDD at any time within 6 months prior to screening.
11. In the judgment of the investigator, the subject is considered at significant risk for suicidal behavior during the course of his/her participation in the study.
12. Has failed to respond to ECT during the current depressive episode.
13. Has received VNS at any time prior to screening.
14. Has dementia, delirium, amnestic, or any other cognitive disorder.
15. Has a clinically significant abnormality on the screening physical examination that might affect safety, study participation, or confound interpretation of study results according to the study clinician.
16. Participation in any clinical trial with an investigational drug or device within the past month or concurrent to study participation.

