21. History of hypothyroidism and has been on a stable dosage of thyroid replacement medication for less than 2 months prior to screening. (Subjects on a stable dosage of thyroid replacement medication for at least 3 months or more prior to screening are eligible for enrollment.)

22. History of hyperthyroidism which was treated (medically or surgically) less than 6 months prior to screening.
23. History of positive screening urine test for drugs of abuse at screening: cannabinoids (if the patient has a legitimate medical prescription for cannabis, patient must agree to abstain during the entirety of the study and to have a negative test at baseline), cocaine, amphetamines, barbiturates, opiates (unless use is in accordance with guidance provided in table of allowed and excluded medications).
24. Patients with exclusionary laboratory values (see Table 1), or requiring treatment with exclusionary concomitant medications (see Appendix 1).
25. Patients on exclusionary concomitant psychotropic medications, the half-life of which would not allow sufficient time for patients to have been free of the medication post-taper for five half-lives within the maximum screening period (28 days).
26. Patients with a history of narrow angle glaucoma.
27. Liver or renal Function tests which meet the exclusion criteria in Table 1, or a history of hepatic or renal dysfunction.

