screening phase to allow proper wash-out at the baseline/randomization visit (e.g., at least 5 half-lives of the drug). The screening period (between the screen visit and baseline visit) can be extended to allow for a clinically appropriate tapering of such medications, again under the close supervision of the study physician, who will see them weekly during the taper phase and to ensure that the discontinuation of the excluded psychotropic medications occurs at least 5 half-lives prior to the baseline visit. The investigator will determine that patients meet eligibility criteria and will collect the demographic and medical data permitting full characterization of the patient.

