#### I.1.c. RANDOMIZATION

For entry into the study and randomization, all eligibility criteria MUST be met (e.g., all inclusion criteria and no exclusion criteria). Patients who meet inclusion/exclusion criteria at the baseline visit (Day 0) will be randomized in a 1:1 fashion to either brexpiprazole plus intranasal ketamine treatment or placebo plus intranasal ketamine. All subjects will be followed for up to 28 days post randomization in order to examine the efficacy, safety, and tolerability of the study drug as well as the durability of the study drug's effects.

Specifically, patients will return for outcome assessments 24 hours after initiating treatment (Day 1), 48 hours after initiating treatment (Day 2), and then every 3 days after that for 26 days, with end of study visit one week after the last double-blind visit. (See Table 3 for the Study Schedule of the events.)

Patients with a MADRS score below 20 at either the screening or baseline visits will be excluded from further participation in the study. Upon determining at the baseline visit (Day 0) that a patient still meets all entry criteria for the study, the patient will be assigned (by study subject number assigned at consent) to the next randomization slot from the randomization list that will have been generated by the MGH Biostatistician.

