## N. DATA ANALYSIS

To analyze the primary outcome data, we will use a linear mixed model for the observations taken at baseline, and subsequent visits, with terms for visit, and visit\*treatment for visits other than baseline, the primary contrast of interest being the difference between the two weeks (Day 14) value for active treatment and placebo. To address missing data, we will use all available data and use a restricted maximum likelihood estimation procedure, as implemented by SAS Proc MIXED. The model will include a site, a site\*time effect and a site\*time\*treatment interaction. The latter will be removed if not significant. Number of comorbid medical and psychiatric disorders and duration of illness, as measured prior to randomization, will be included as covariates. For the continuous secondary efficacy variables, the same approach as for the primary efficacy variable will be used for the analysis.

Power analysis: the sample size was chosen to ensure 80% power to detect an effect size of 0.8 on the SDQ between brexpiprazole plus intranasal ketamine treatment and placebo at a two-sided 0.05 significance level. This assumes the randomization of 52 subjects (26 subjects per arm).

O. PROTOCOL SIGNATURE PAGE

I have read this protocol and agree to adhere to the requirements. I will provide copies of this protocol and all pertinent information to the study personnel under my supervision. I will discuss this material with them and ensure they are fully informed regarding the conduct of the study according to 21 CFR parts 50, 54, 56 and 812, 45 CFR 46, to GCP as described in ICH guideline E6 and to hospital Institutional Review Boards.

\_\_\_\_\_  
Clinical Site

\_\_\_\_\_  
Principal Investigator Signature

\_\_\_\_\_  
Date

\_\_\_\_\_  
Principal Investigator  
Printed Name

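### No exclusion covers an earlier failed course of brexpiprazole in the current episode, or known intolerance of brexpiprazole or ketamine

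*Combined protocol and SAP*

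**What the plan says.** Inclusion criterion 4 (H.2.a) requires at least two failed treatment courses in the current episode, and exclusion 4 (H.2.b) sets the ceiling at seven. Neither names a drug. Two exclusions concern a specific earlier treatment. Criterion 12 removes a patient who "Has failed to respond to ECT during the current depressive episode", and criterion 13 removes anyone with any past VNS.

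Section D.2.b says of brexpiprazole: "The drug was recently approved by the US FDA for adjunctive therapy with antidepressant treatment (ADT) in patients with major depressive disorder (MDD"). The approval is for those whose antidepressant has not worked well enough, which is close to the population recruited here.

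The remaining controls on drugs govern current use or recent research participation:

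- Appendix 1 bars antipsychotics and ketamine as concomitant medication.
- Inclusion 4 bars antipsychotics as the background antidepressant.
- Exclusion 16 covers trial participation within the past month.
- Exclusion 24 covers patients who require a barred drug.
- Exclusion 25 sets a 28-day limit and removes patients on a barred psychotropic "the half-life of which would not allow sufficient time for patients to have been free of the medication post-taper for five half-lives".

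Section I.1.a otherwise lets a barred psychotropic be tapered during screening, under supervision, "to ensure that the discontinuation of the excluded psychotropic medications occurs at least 5 half-lives prior to the baseline visit". Eligible patients are then "randomized in a 1:1 fashion to either brexpiprazole plus intranasal ketamine treatment or placebo plus intranasal ketamine" (I.1.c).

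**The concern.** None of the 10 inclusion or 27 exclusion criteria mentions earlier non-response to, or intolerance of, either study drug. Two kinds of patient can pass through the gap. One took an adequate course of adjunctive brexpiprazole earlier in this episode without success and has stopped it; no washout is needed. The other is still taking it and is tapered during screening. Either has a one-in-two chance of being assigned brexpiprazole again.

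Two things are at stake. First, a patient who did not respond to brexpiprazole before is less likely to show a brexpiprazole–placebo difference on the SDQ at Day 14, so each such patient tends to shrink the primary contrast. Nothing later in the plan compensates. I.1.c mentions no stratification by prior exposure, the covariates in section N are comorbidity counts and duration of illness, and J.6.a says that patients who discontinue are not replaced. Second, a patient with known intolerance would be re-exposed: to brexpiprazole with probability one half, and to ketamine with certainty, because both arms receive it.

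**Working it through.** **Inputs from the documents (section N).** The plan states that "the sample size was chosen to ensure 80% power to detect an effect size of 0.8 on the SDQ" at a "two-sided 0.05 significance level", with 52 patients, 26 per arm. No SD, dropout allowance or rate of prior brexpiprazole use is given.

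**Step 1: reproduce the plan's figure.** Two-sample t-test with n = 26 per arm and d = 0.8:

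- degrees of freedom 2 × 26 − 2 = 50; critical value 2.009
- noncentrality d × √(n/2) = 0.8 × √13 = 2.884
- power 80.7%

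Twenty-six is the smallest n per arm that reaches 80%. At 25 per arm, the figure given under Table 2 in section I.1, power is 79.1%. The plan's number is reproduced, with less than one percentage point to spare.

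**Step 2: dilution.** Let f be the share of randomised patients who gain nothing from brexpiprazole because they have already failed it. The average effect is then d(f) = 0.8 × (1 − f). The value of f is an assumption.

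| f (assumed) | d(f) | Noncentrality | Power at 26 per arm | Total N for 80% |
|---|---|---|---|---|
| 0% | 0.800 | 2.884 | 80.7% | 52 |
| 2% | 0.784 | 2.827 | 79.2% | 54 |
| 5% | 0.760 | 2.740 | 76.6% | 58 |
| 10% | 0.720 | 2.596 | 72.1% | 64 |
| 20% | 0.640 | 2.308 | 61.9% | 80 |

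In patients, 10% is about 5 of the 52 randomised (0.10 × 52 = 5.2), or about 3 in the brexpiprazole arm (2.6). Twenty per cent is about 10 (10.4), or about 5 in that arm (5.2).

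**Step 3: partial benefit.** If prior failures keep half the effect, the loss is halved: d = 0.8 × (1 − f/2). At f = 10% that gives 0.76 and 76.6%. At f = 20% it gives 0.72 and 72.1%.

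**Step 4: extra spread.** Mixing patients with and without benefit adds f(1 − f) × 0.8² to the active-arm variance, taking the common SD as 1. Averaging the two arms' variances lowers the powers in the table slightly, to 78.9%, 76.0%, 70.9% and 59.8% for f = 2%, 5%, 10% and 20%. The picture does not change.

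**Step 5: ketamine.** Ketamine is common to both arms, so earlier failure of ketamine does not enter d(f). The table concerns brexpiprazole only.

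**Step 6: is the washout route open?** Exclusion 25 requires five half-lives within 28 days, so a half-life of at most 28/5 = 5.6 days before any taper time. The documents give no half-life for brexpiprazole. I.1.a also says that screening can be extended for tapering, which does not fit the 28-day maximum; the two passages should be reconciled. The route through an earlier, already stopped course depends on neither.

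**The case against.** The case against rests on size and reach, and several parts of it stand.

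- **Frequency is unknown.** D.2.b describes the approval as recent, so prior use may be rare. Use is also not failure, and a rate of prior use cannot be put in for f. This stands, and it is why the table starts at 2% and is only illustrative.
- **Current use is not failure.** A reader might infer that anyone taking brexpiprazole at screening with a MADRS of 20 or more is a known non-responder. The documents do not support that. Their own standard for failure (inclusion 4) needs adequate dose and duration, and the patient may have just started.
- **Earlier failure does not mean no effect here.** A reader might infer that prior non-responders cannot contribute to a positive result. The hypothesis concerns brexpiprazole combined with ketamine, and failure is defined as under 50% improvement, which leaves room for partial benefit. Zero benefit is the worst case.
- **ECT and VNS are not a precedent.** It is tempting to call the criteria internally inconsistent. But H.3 gives no specific reason for criteria 12 and 13, and criterion 13 excludes any VNS exposure, not failure. They show that the protocol uses treatment history, and no more.
- **Existing safeguards.** Washout of five half-lives leaves about 3% of the drug (0.5⁵ = 0.031) under first-order elimination, so a strong claim about residual drug at baseline is not warranted. Dose step-down (J.4), supervised ketamine dosing (I.1.d) and medical monitoring (M.7) limit harm from intolerance. Except where an eligibility query happens to raise it, they act only after re-exposure.
- **Validity.** Randomisation keeps the comparison fair. Dilution pulls the estimate towards no difference and does not create a false positive.

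What does not stand is the suggestion that the existing criteria already cover these patients. Investigator judgement may catch some, but no criterion requires it.

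**Conclusion.** The gap is real and worth closing. Patients with an inadequate response to an adequate course of brexpiprazole in the current episode, or with known intolerance of either study drug, are eligible as the criteria are written.

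The effect on the primary analysis is a possible loss of power, not bias in favour of the drug. Its size cannot be determined from the documents. With no benefit in a share f of patients, the loss from 80.7% would be 1.5 percentage points at f = 2%, 4.1 at 5%, 8.6 at 10% and 18.8 at 20%, and less with partial benefit. These figures assume the plan's own effect size of 0.8, a simple two-sample comparison and no dropout. They matter mainly because the sample size has almost no slack.

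A reader might extend the dilution argument to prior ketamine failure. That does not follow, because ketamine is given in both arms; for ketamine the point is avoidable re-exposure of patients known not to tolerate it.

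**What to change.** Add one criterion to H.2.b, for example: *Inadequate response to an adequate course of brexpiprazole during the current episode, or known intolerance of or hypersensitivity to brexpiprazole or ketamine.*

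The criterion should not extend to any use of these drugs in the episode, or to non-response at any time in life. Either would remove partial responders, inadequate trials and old episodes, which the argument does not reach.

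Check it from the medical and medication history already taken at screening. Add a direct question on these two drugs alongside the MGH ATRQ interview. I.2.d describes that instrument as an antidepressant history, and nothing says that it captures brexpiprazole, ketamine or intolerance, so it should not be relied on alone.

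The cost is one criterion and one question, a few more screen failures and a slightly narrower population. If the sponsor prefers to keep earlier brexpiprazole failures, to learn whether the combination helps them, the protocol should say so, record prior exposure and response at screening, and prespecify a sensitivity analysis without them.

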**TABLE 1-EXCLUSIONARY SAFETY VALUES OF POTENTIAL CLINICAL CONCERN**

Hematology	
Leukocytes	<2 or >17.5 x 10  /mm 
Platelets	<75 or >700 x 10  /mm 
Chemistry	
Total bilirubin	>2 times the upper limit of the reference range
AST*	>2.5 times upper limit of the reference range
ALT*	>2.5 times upper limit of the reference range
GGT*	>2.5 times upper limit of the reference range
Alk Phosphatase*	>2.5 times upper limit of the reference range
Creatinine	>1.3 times upper limit of the reference range
BUN/Urea	>1.3 times upper limit of the reference range
Glucose	< 70 mg/dl or >2 times the limits of the reference range
Uric acid	>1.5 times upper limit of the reference range

\*LFTs higher than 2.5 times ULN will be exclusionary.

### H.3. RATIONALE FOR THE INCLUSION/EXCLUSION CRITERIA

Eligibility criteria for this study have been carefully considered to ensure the safety of the study subjects and to ensure that the results of the study are meaningful in support of the research hypotheses. It is imperative that subjects fully meet all eligibility criteria.

## I. STUDY ASSESSMENTS – PLAN AND METHODS

### I.1. STUDY CONDUCT

An overview of the schedule of visits and procedures is shown in Table 2.

**TABLE 2– OVERVIEW OF STUDY SCHEDULE**

Screen Visit	Screening Period	V1 / Baseline Visit	V2	V3	V4	V5	V6	V7	V8	V9	V10	V11
Day -28 to Day -7	Taper (opt.) 5 half-lives of excluded psychotropic drug(s)	Day 0	Day 1	Day 2	Day 5	Day 8	Day 11	Day 14	Day 17	Day 21	Day 23	Day 28
		Baseline Assess.	Assess.	Assess.	Assess.	Assess.	Assess.	Assess.	Assess.	Assess.	Assess.	Assess.
		Intranasal Ketamine Admin.	Assess.	Assess.	Intranasal Ketamine Admin.	Intranasal Ketamine Admin.	Intranasal Ketamine Admin.	Intranasal Ketamine Admin.	Assess.	Intranasal Ketamine Admin.	Assess.	Assess.
		Study Drug*	Study Drug*	Study Drug*	Study Drug*	Study Drug*	Study Drug*	Study Drug*	Study Drug*	Study Drug*	Study Drug*	Study Drug*

\*Brexipiprazole or Placebo

Subjects will be screened for eligibility as detailed above. Study participants will be consented prior to the administration of any procedure or wash-out. Following a washout period, under the close supervision and monitoring of the study clinicians, for patients on psychotropic drugs (with the exception of ongoing antidepressant therapy and of ongoing hypnotic therapy), baseline assessment, MGH CTNI remote interview, and re-confirmation that all criteria for entry into the study are met, eligible subjects will be randomly assigned to one of two arms: brexpiprazole plus intranasal ketamine (n=25) or placebo plus intranasal ketamine (n=25). The brexpiprazole dose will be titrated in the following manner: 0.5 mg/day during the first week, at the Visit 5/Day 8 visit, the dose will be increased to 1 mg/day, at Visit 7/Day 14 the dose will be increased to 2 mg/day, and at Visit 9/Day 21, the dose will be increased to 3 mg/day. If the dose escalation is not tolerated, patient can go back to previous dose (fixed-flexible dose escalation). As per Table 2, all subjects will be followed for 28 days to examine the efficacy and tolerability of brexpiprazole plus intranasal ketamine’s effects. The study assessments will be performed at Days 0, 1, 2, 5, 8, 11, 14, 17, 21, 23, and 28 to assess the safety and efficacy of brexpiprazole plus intranasal ketamine compared to placebo plus intranasal ketamine treatment therapy in depressed patients who have demonstrated an inadequate response

to at least 2 adequate antidepressant therapies (ADTs) during the current MDE. Intranasal ketamine (40 mg) will be administered after all the assessments are completed on Days 0, 5, 8, 11, 14, and 21.

#### I.1.a. SCREENING PHASE

The screening period will range from a minimum of 7 days to a maximum 28 days. The purpose is to ensure that only appropriate patients are entered into the study. The investigator will determine that the patients meet eligibility criteria and will collect the demographic and medical data permitting full characterization of the patients. The screening period is also designed to ensure that any prohibited pharmacotherapy is washed out. Benzodiazepine therapy is allowed per the requirements in Appendix I. The screening period begins when informed consent is signed. Screening evaluations are to be conducted as outlined in the Study Schedule (

#### TABLE 3– STUDY SCHEDULE

).

The screening period will range from a minimum of 7 days to a maximum of 28 days. The screening period begins when informed consent is signed. Only the study physicians will perform the informed consent procedures. Once patients agree to participate in the study by signing the informed consent document, a full medical and psychiatric history will be taken and a physical and laboratory examination will be performed, as outlined in the Table 3.

Only patients currently on stable antidepressant therapy will be eligible for the study. During screening, investigators must document history during the *current* episode of inadequate response to at least 2 trials of antidepressant treatment of adequate dose and duration, as specified by the MGH ATRQ (Fava and Davidson, 1996; Fava, 2003; Chandler et al, 2010). Such determination will be confirmed by the remote, independent MGH CTNI raters.

We have observed in 3 multi-center trials recently completed by the MGH CTNI that the placebo responses among subjects who have not responded to antidepressant therapy and are still on the antidepressant at the time of the screening assessment are comparable or even lower than the placebo response rates reported in trials with the prospective determination of resistance, such as the aripiprazole augmentation trials (Fava et al, 2010; Fava et al, 2012; Nelson et al, 2009).

The screening period is also designed to allow the gradual taper and discontinuation of the ongoing excluded psychotropic drugs so that any prohibited psychotropic medication is washed out under supervision of a study physician. The study physician and/or site staff will maintain ongoing telephone contact with the patient during the washout period in order to ensure patient safety during this time. Patients will discontinue their excluded psychotropic drugs documented during the

screening phase to allow proper wash-out at the baseline/randomization visit (e.g., at least 5 half-lives of the drug). The screening period (between the screen visit and baseline visit) can be extended to allow for a clinically appropriate tapering of such medications, again under the close supervision of the study physician, who will see them weekly during the taper phase and to ensure that the discontinuation of the excluded psychotropic medications occurs at least 5 half-lives prior to the baseline visit. The investigator will determine that patients meet eligibility criteria and will collect the demographic and medical data permitting full characterization of the patient.

